3.5 Dose Justification

In order to identify a potential starting dose in the Phase 2 clinical trial in adult patients with COVID-19 using the existing data, toxicology data from the 14-day dog toxicology study were relied on; these are considered to be the most appropriate as the NOAEL in rats (50 mg/kg) is much less sensitive than the dog. In the 14-day dog toxicology study, the NOAEL dose was established as 2.5 mg/kg/day. The FDA’s Guidance for Industry entitled “Estimating the Maximum Safe Starting Dose in Initial Clinical Trials for Therapeutics in Adult Healthy Volunteers” (FDA, 2005) was used to determine the human equivalent dose (HED) for an infected

adult weighing 70 kg. This patient represents the mid-range of the weight of COVID-19 patients intended to be included in the Phase 2 trial. The dog NOAEL dose of 2.5 mg/kg/day converts to a HED of 1.4 mg/kg/day. Applying a safety factor of 10 results in an initial starting dose of approximately 0.14 mg/kg/day or 10 mg/day. The study dose of 5 mg over 2 hours is substantially less than the HED and safe according to the Phase 1 results.

4 STUDY OBJECTIVES AND ENDPOINTS

4.1 Study Objectives

4.1.1 Primary Objective

To evaluate the proportion of subjects alive and free of respiratory failure (*e.g.*, need for non-invasive or invasive mechanical ventilation, high flow oxygen [≥ 6 L/minute], or ECMO) and free of the need for continued renal replacement therapy (RRT) on Day 28. The need for continued RRT at Day 28 will be defined as either dialysis in the past 3 days (Day 26, 27, or 28) or an eGFR¹ on Day 28 <10 mL/min/1.73 m².

4.1.2 Secondary Objectives

To evaluate the following:

- Incidence and time to mild, moderate, and severe ARDS between treatment groups
- Ventilation-free days
- Time on nasal canula or oxygen mask
- 28-day mortality— both all-cause and attributable
- ICU length of stay (in days)
- Hospitalization length of stay (in days)
- Virologic clearance rate
- Incidence of other organ disorders
- Need and duration for extracorporeal membrane oxygenation (ECMO)
- Vasopressor-free days
- Clinical improvement in chest x-rays
- Change in baseline modified Medical Research Council (mMRC) dyspnea scale
- SOFA scores assessed periodically
- Change from baseline in liver function tests (ALT, AST, and/or total bilirubin)
- Change from baseline in SCr and eGFR

¹ eGFR is calculated from the serum creatinine according to the eGFR_{CKD-EPI} equation (Levey *et al*, 2009):
$$\text{eGFR (mL/min/1.73 m}^2\text{)} = 141 \times \min(S_{\text{cr}}/\kappa, 1) \alpha \times \max(S_{\text{cr}}/\kappa, 1) - 1.209 \times 0.993 \text{Age} \times 1.018 \text{ [if female]} * 1.159 \text{ [if black], where } S_{\text{cr}} = \text{serum creatinine; } \kappa = 0.7 \text{ for females and } 0.9 \text{ for males; } \alpha = -0.329 \text{ for females and } -0.411 \text{ for males; min indicates the minimum of } S_{\text{cr}}/\kappa \text{ or } 1, \text{ and max indicates the maximum of } S_{\text{cr}}/\kappa \text{ or } 1.$$

- Change from baseline in highly-sensitive troponin (hs-troponin)
- Change from baseline ACT, aPTT, and/or PT/INR levels
- Change from baseline for antiviral immunoglobulins (IgG, IgM, and IgA) at EOS.

4.1.3 Health Outcomes Objective

- Total healthcare costs from admission to discharge (Omer *et al*, 2020).

4.1.4 Exploratory Objectives

- Change in serum cytokines including IL-1 α , hs-troponin, and ferritin levels, as well as other exploratory biomarkers drawn at the same time as LSALT peptide levels.
- Change in baseline antiviral immunoglobulins (IgG, IgM, IgA) at EOS.
- Pharmacokinetics of LSALT peptide and fragments (metabolites) over the study period.

4.2 Study Endpoints

4.2.1 Primary Efficacy Endpoint

To evaluate the proportion of subjects alive and free of respiratory failure (*e.g.*, need for non-invasive or invasive mechanical ventilation, high flow oxygen [≥ 6 L/min], or ECMO) and free of the need for continued renal replacement therapy (RRT) on Day 28. The need for continued RRT at Day 28 will be defined as either dialysis in the past 3 days (Day 26, 27, or 28) or an eGFR on Day 28 <10 mL/min/1.73 m 2 .

4.2.2 Secondary Efficacy Endpoints

Secondary efficacy endpoints include:

- All-cause mortality
- The presence and severity of ADRS as an ordinal outcome of the proportion of patients who have none, mild, moderate, or severe ARDS
- Time to each of mild, moderate, and severe ARDS
- The number of ventilation-free days and ECMO-free days
- Time on nasal canula or oxygen mask
- Length of stay in ICU and hospital (admission to discharge)
- Virologic clearance rate
- Worst PaO₂/FiO₂ ratio following enrollment
- Change in PaO₂/FiO₂ ratio
- Vasopressor-free days
- Change from maximal radiographic damage to EOT
- Change in baseline mMRC score

- Change in APACHE II score
- Proportion of patients with extrapulmonary organ dysfunction using the daily SOFA score
- Change in liver function tests (ALT, AST, total bilirubin)
- Change in renal function tests (SCr, eGFR)
- Change in hs-troponin levels
- Change in ACT, aPTT, and/or PT/INR values
- Change in antiviral IgG, IgA, and IgM levels.

4.2.3 Health Outcomes endpoint:

- Total healthcare costs from admission to discharge between treatment groups.

4.2.4 Exploratory Endpoints:

- Change in serum cytokines including IL-1 α , IL-1 β , and ferritin levels, as well as other exploratory biomarkers drawn at the same time as LSALT peptide concentrations.
- Change in baseline antiviral immunoglobulins (IgG, IgM, IgA) at EOS.

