9.3.2 Efficacy Analyses

The primary efficacy endpoint is the proportion of subjects alive and free of respiratory failure (*e.g.*, need for non-invasive or invasive mechanical ventilation, high flow oxygen (≥ 6 L/minute), or ECMO) and free of the need for continued renal replacement therapy (RRT) on Day 28. The need for continued RRT at Day 28 will be defined as either dialysis in the past 3 days (Day 26, 27, or 28) or an eGFR on Day 28 <10 mL/min/1.73 m².

Analyses for the primary and the key secondary endpoints will be performed on the FAS and PP populations, with the analysis on the FAS as the primary analysis; all other efficacy endpoints will be analyzed on the FAS population only.

Time to event variables will be summarized using Kaplan-Meier survival curves and compared between treatment groups using either Log-rank tests or Cox's Proportional Hazard model adjusting for baseline covariates, as necessary. For continuous variables assessed at multiple time points a Mixed Model Repeated Measures (MMRM) approach will be used or Analysis of Covariance (ANCOVA) if assessed at a single time point post-baseline. For categorical endpoints Cochran-Mantel-Haenszel (CMH) methods will be used, or a logistic regression approach, in the case of continuous covariates.

Additional details regarding precise endpoint definitions (including transformations, as applicable), analysis model specifications and alpha-level control for primary and important secondary endpoints associated with multiplicity will be provided in the SAP, to be finalized prior to unblinding the study.

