9.3.7 Missing Data

Although significant missing data with respect to the primary endpoint is not anticipated for a study of this duration (due to the nature of the endpoint), methods for handling missing data and intercurrent events, including for secondary endpoints will be specified in the SAP. These methods will be consistent with missing data due to death as having a worst possible outcome.

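### Time on nasal cannula or mask also stops at ventilation or death, so a drug that prevents those events can lengthen it and look worse

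*Combined protocol and SAP*

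**What the plan says.** Sections 4.2.2 and 7.1.2 list "Time on nasal canula or oxygen mask" among the secondary efficacy endpoints. They give no direction of benefit and no rule for a patient who moves to ventilation or dies. ICU and hospital stay are listed in the same way, as raw durations running to discharge. Section 4.1.3 adds "Total healthcare costs from admission to discharge". None of these says what happens when a patient dies before discharge.

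The same list uses a different form for other kinds of support: "The number of ventilation-free days and ECMO-free days", and vasopressor-free days.

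On death and intercurrent events, 9.3.7 says that "methods for handling missing data and intercurrent events, including for secondary endpoints will be specified in the SAP", and then: "These methods will be consistent with missing data due to death as having a worst possible outcome". The Synopsis says the same. Section 9.3.2 also leaves precise endpoint definitions to the SAP, to be final before unblinding. No SAP text is in the file. For time-to-event variables, 9.3.2 says "Time to event variables will be summarized using Kaplan-Meier survival curves", with log-rank or Cox comparisons. It names no competing-risk method and no rule for censoring at death.

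**The concern.** Cannula or mask time stops for one good reason, recovery, and for two bad ones, escalation to ventilation and death. The trial hopes to prevent the two bad ones, and both count as failures in the primary endpoint. A patient intubated on Day 3 contributes a short oxygen time. The same patient, had the drug worked, might contribute a full course of a week or more. The arm difference therefore mixes recovery with deterioration and can point against an effective drug.

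The death principle does not settle this. A three-day oxygen time ended by intubation is neither missing nor due to death. A duration ended by death may also be recorded as an observed short value, so it is unclear that the principle applies there.

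This is a 60-patient proof-of-concept trial whose size rests on medical judgement (9.1). The direction of its secondary endpoints will be part of what informs further study.

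**Working it through.** **Source of the event rates.** Section 9.3.6.1 assumes unfavourable primary outcomes of 28% on placebo and 22.4% on LSALT, and puts the chance of crossing each DSMB boundary at about 6% or less. With two independent binomials, and 6, 18 and 60 read as total subjects:
- 3 per arm, difference of at least 2: 5.3%
- 9 per arm, difference of at least 3: 4.9%
- 30 per arm, difference of at least 4: 6.1%

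The stated figure is reproduced, so these rates are used below. The plan gives no figure for the endpoints at issue.

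**Oxygen time, simple form.** If the drug acts only by preventing events, then

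LSALT − placebo = (0.224 − 0.28) × (mean oxygen days with an event − mean oxygen days without).

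The documents give no durations, so a range is assumed: 7 to 14 days without an event, 2 to 12 with one.
- 14 versus 2 days: −0.056 × (2 − 14) = +0.67 days
- 10 versus 4 days: −0.056 × (4 − 10) = +0.34 days
- 7 versus 12 days (long oxygen use after extubation): −0.056 × (12 − 7) = −0.28 days

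The sign goes against LSALT whenever an event shortens total oxygen time. If every patient with an event is instead given 28 days, the differences are −1.18, −1.01 and −0.78 days for event-free times of 7, 10 and 14 days. All favour LSALT.

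**Oxygen time, simulation.** 20,000 trials, 30 per arm. Assumptions:
- Events are half deaths and half ventilated survivors.
- Recoverers: oxygen time lognormal, median 6 days, log-SD 0.5, so the mean is 6 × exp(0.125) = 6.80.
- Patients with an event leave the cannula uniformly between Day 1 and Day 4, mean 2.5.
- For oxygen-free days, deaths score 0 and ventilated survivors count as on support until discharge.

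Expected difference: 0.14 × (6.80 − 2.5) = +0.60 days if events are halved (28% to 14%), and 0.056 × 4.30 = +0.24 days at 28% versus 22.4%. The simulated standard error is about 0.95 days.

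If ventilated survivors resume oxygen (lognormal, log-SD 0.5), half the events gain that time. With a median of 7 days the event mean becomes 2.5 + 0.5 × 7.93 = 6.47, and the differences shrink to 0.14 × 0.33 = +0.05 and 0.056 × 0.33 = +0.02 days.

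| Share of trials in which LSALT looks worse | Events halved | 28% vs 22.4% |
|---|---|---|
| Oxygen time, no return to oxygen | 74% | 60% |
| Oxygen time, return, median 5 days | 59% | 53% |
| Oxygen time, return, median 7 days | 52% | 51% |
| Oxygen-free days, death = 0 | about 12% | about 33% |

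**Hospital stay.** Assumed stay: recoverers median 9 days (log-SD 0.5, mean 10.20), ventilated survivors median 22 (log-SD 0.3, mean 23.0), deaths uniform between Day 4 and Day 20 (mean 12).
- Events halved: −0.07 × (12 − 10.20) − 0.07 × (23.0 − 10.20) = −1.0 day. Stay is longer on LSALT in 28% of trials.
- 28% versus 22.4%: −0.4 day, longer on LSALT in 41%.
- Mortality 20% versus 10%, ventilation absent or equal in both arms: −0.10 × 1.80 = −0.2 day. Stay is longer on LSALT in about 45%, while hospital-free days look worse in about 20%.

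A wider grid at 28% versus 22.4% takes 8 to 12 days event-free, death at Day 5 to 16, and 20 to 28 days for ventilated survivors. With 40% or 52.4% of events fatal (52.4% is the ARDS case fatality quoted in 3.2), all 36 combinations give a shorter stay on LSALT, by 0.01 to 0.85 days. The sign reverses (+0.11 to +0.39) only when every event is a death before the usual discharge day.

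ICU stay and costs were not simulated.

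**The case against.** **The SAP may deal with it.** Intubation and death during an oxygen-time endpoint are intercurrent events, and the protocol promises methods for these, and precise endpoint definitions, before unblinding. This stands in part: a reader might infer that the plan ignores death and escalation, and it does not. But the only principle it commits to is worded for data missing due to death. The choice of a raw duration is already made in 4.2.2 and 7.1.2, beside endpoints in free-days form.

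**The size depends on assumed durations.** This stands. The 74% needs a halving of events, well beyond the protocol's 20% relative reduction, and no return to oxygen after extubation. With a median 7-day return the distortion nearly vanishes. The shift is also small beside the noise: with an assumed SD of 5 to 9 days, the standard error at 30 per arm is 1.3 to 2.3 days.

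**Stay and costs.** A reader might infer that intubation shortens these too, so that they would reverse like oxygen time. The documents do not support that. Both run to discharge, and a ventilated survivor plausibly stays longer, so preventing intubation moves stay in the drug's favour. Only early death shortens them, and mean stay favoured LSALT in every simulated scenario. Stay and cost are also legitimate measures of resource use.

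**Other endpoints would expose the problem.** All-cause mortality, ventilation-free days and the primary composite are reported alongside. That limits the harm but does not make raw oxygen time a sound efficacy comparison.

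**Conclusion.** The point holds for oxygen time. As defined, it can move against a drug that prevents ventilation or death, and no rule in the protocol clearly prevents this. Under the assumed durations it looks worse on LSALT in 51% to 60% of trials at the protocol's own effect, and in 52% to 74% if events are halved. Oxygen-free days look worse in about 33% and 12%. Even where the distortion is near zero, raw time therefore carries almost no information about benefit, while the free-days form does.

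For hospital stay the conclusion is weaker: signal is lost when deaths end stays early (about 45% against about 20% in the mortality scenario), without a reversal of the mean. For ICU stay and costs the same reasoning about early death applies, but no size is claimed.

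The figures rest on assumed durations, an even split of events into deaths and ventilated survivors, and a drug that acts only by preventing events. They also use the 28% rate as a proxy. That rate refers to the Day 28 composite, which includes high-flow oxygen and renal replacement as well. The primary endpoint is not affected. This should be corrected before unblinding; it does not threaten the trial's main conclusion.

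**What to change.** In 4.2.2, 7.1.2 and the SAP, and in the matching Synopsis list:
- Replace oxygen time with days alive and free of any supplemental oxygen or ventilatory support through Day 28, with death scored 0. Keep raw cannula or mask time as a descriptive summary.
- For the efficacy comparison of stay, use ICU-free and hospital-free days through Day 28, with death scored 0.
- Report raw ICU stay, hospital stay and costs descriptively, by survival status.

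The cost is endpoint and SAP wording; the same data are used. The small downside is that free-day scores are less direct as a measure of resource use, which is why the raw values stay in the report.

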- Incidence and time to mild, moderate, and severe ARDS per patient between treatment groups
- Ventilation-free days
- Time on nasal canula or oxygen mask
- 28-day mortality— both all-cause and attributable
- ICU length of stay (in days)
- Hospitalization length of stay (in days)
- Virologic clearance rate
- Incidence of other organ disorders
- Need and duration for extracorporeal membrane oxygenation (ECMO)
- Vasopressor-free days
- Clinical improvement in chest x-rays
- Change in baseline modified Medical Research Council (mMRC) dyspnea scale
- SOFA scores assessed periodically
- Change from baseline in liver function tests (ALT, AST, and total bilirubin levels)
- Change from baseline in SCr and eGFR
- Change from baseline in highly-sensitive troponin (hs-troponin)
- Change from baseline ACT, aPTT, and/or PT/INR levels
- Change from baseline for antiviral (SARS-CoV-2) immunoglobulins; IgG, IgM, and IgA at EOS.

HEALTH OUTCOMES OBJECTIVE:

- Total healthcare costs from admission to discharge.

EXPLORATORY OBJECTIVES: To evaluate:

- Change in serum cytokines including IL-1 α , IL-1 β , and ferritin levels, as well as other exploratory biomarkers.
- Change in baseline antiviral immunoglobulins (IgG, IgM, IgA) at EOS.
- Pharmacokinetics of LSALT peptide over the study period.

STUDY DESIGN AND METHODOLOGY: This study is a parallel group, randomized, third-party blinded, multicenter study to assess safety and efficacy of LSALT peptide *versus* placebo in hospitalized patients with confirmed infection or recent confirmed infection with complications associated with COVID-19.

Patients will be followed for safety and efficacy up to Day 28, with Day 1 being the day of randomization to assess safety.

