5.3 Discussion of Study Design

This double-blind, placebo-controlled, proof-of-concept Phase 2 study is designed to evaluate LSALT peptide compared with placebo in a defined number of adult hospitalized patients with the diagnosis of COVID-19. This is a 1:1 randomization comparing 5 mg LSALT peptide daily with matching placebo. LSALT peptide or drug-free saline will begin immediately once the patient meets all inclusion/exclusion criteria at the start of hospitalization and followed with physical and respiratory exams, blood chemistries, coagulation, hematology, ECGs, SARS-CoV-2 tests, CXRs, biomarkers, and PK will be recorded periodically throughout the 28 day study. When clinically indicated, questionnaires (APACHE II, SOFA) will be obtained at Baseline, EOT, and EOS; venous blood gas (VBG) or HCO_3 (bicarbonate) levels may be substituted for arterial blood gas (ABG) if it is SOC or in the patient's best interest, and results in comparable APACHE II and SOFA scores (Brown *et al*, 2016). Other questionnaires (Berlin Definition and modified Medical Research Council Dyspnea Scale) will be assessed at Baseline, Day 3, EOT, and EOS. Patients will be maintained on SOC, including prophylaxis or treatment for VTE, per institutional guidelines throughout the study. Dosing will end on Day 14, or at cure or increasing severity of ARDS, or at death. Patients will be followed clinically, and safety and efficacy measures will be recorded at end of study (EOS; Day 28) or death, whichever occurs first.

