5.4 Selection of Study Population

5.4.1 Inclusion Criteria

Eligible patients must fulfill the following inclusion criteria:

1. Male or female hospitalized patients between 18 and 80 years of age at time of consent.
2. Clinical and laboratory diagnosis of COVID-19 infection. Patients must be positive for the SARS-CoV-2 by Real-Time Reverse Transcriptase (RT)-PCR Diagnostic Panel or have an existing complication secondary to SARS-CoV-2 infection which was positive within 2 weeks of entry into the study. Further, patients must have at least two of the following three symptoms:
 - Fever (oral temperature $\geq 100.4^{\circ}\text{F}$ [$> 38^{\circ}\text{C}$]) with or without chills
 - Dyspnea or difficulty breathing (≥ 2 on mMRC dyspnea scale)
 - Nonproductive cough (Stokes *et al*, 2020),
 - Or other signs and symptoms of established complications to SARS-CoV-2 infection (*e.g.*, coagulopathy, cardiomyopathy, acute kidney injury [AKI], and/or acute liver injury) within the limits of Exclusion Criteria #8.
3. Patients must present with moderate to severe illness as defined below:
 - Moderate illness: Patients who have evidence of lower respiratory disease by clinical assessment or imaging and an oxygen saturation (SpO_2) $> 93\%$ on room air at sea level
 - Severe illness: Patients who have a respiratory frequency > 30 breaths per minute (bpm), $\text{SpO}_2 \leq 93\%$ on room air at sea level, ratio of arterial partial pressure of oxygen to fraction of inspired oxygen ($\text{PaO}_2/\text{FiO}_2$) < 300 , or lung infiltrates $> 50\%$ (COVID-19 Treatment Guidelines Panel, 2020).
4. APACHE II score < 20 or establishment of survivability of the patient beyond 48 hours

following randomization.

5. Therapies which have been shown to be beneficial and are included in standard-of-care COVID-19 treatment guidelines (e.g., those of WHO or NIH, or institutional guidelines) are permitted.

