8 STUDY PROCEDURES AND FLOW CHART

8.1 Study Flow Chart

Calendar	Admission ^a	Admission ^b	Treatment Period	Treatment Period	EOT	EOS
Day	1	1	1 – 14 (max)	3	Variable	28±3
Sign informed consent	X					
Assign screening number	X					
Inclusion/exclusion criteria	X					
Review demographics	X					
Review medical history	X					
Concomitant meds ^c	X		X	X	X	X
Physical exam ^c	X		X	X	X	X
Respiratory exam ^c	X		X	X	X	X
Urine pregnancy in WCBP	X					
Clinical labs/Urine tests ^{c,d}	X			X	X	X
12-lead ECG ^e	X			X	X	X
Vital signs ^{c,f}	X		X	X	X	X
eGFR ^{b,d}	X			X	X	X
SARS-CoV-2 testing swabs ^{c,g}	X			X	X	X
Chest x-ray ^h		X		X	X	X
PK and biomarker samples ⁱ		X		X	X	X
Randomization		X				
Study drug administration		X	X	X	X	X
AE assessments		X	X	X	X	X
SARS-CoV-2 IgG, IgA, IgM levels		X				X
Berlin Definition ^{j,k}		X		X	X	X
SOFA score ^{j,l}		X		X	X	X
mMRC score ^{j,m}		X		X	X	X
APACHE II score ^{j,n}		X		X	X	X
Health Outcomes						X

^a Screening to determine eligibility (prior to randomization)

^b Baseline after Screening and prior to the start of study drug unless otherwise indicated.

^c Performed at Screening, Day 3, and EOT prior to drug administration, and at EOS.

^d Hematology, biochemistry, coagulation, and urinalysis will be obtained and eGFR will be calculated (Appendix 2), and when clinically indicated.

^e 12-Lead ECG (supine) will be recorded at time 0 (pre-dose) at Screening, Day 3, EOT, and at EOS (only if clinically indicated). Also, an ECG will be obtained during the study when clinically indicated.

^f Blood pressure (supine), pulse rate (supine), body temperature, respiration rate (supine), actual body weight (kg), and height (cm). Note: Height will only be measured at Screening.

^g Swabs (nasal, throat, sputum, or lower respiratory tract) at Screening, Day 3, EOT, and EOS.

^h Chest x-rays at Baseline (Day 1), Day 3, at time of clinical improvement, at EOT, and EOS. A chest x-ray will also be obtained if clinically warranted and recorded in the eCRF.

ⁱ Blood draws at Baseline pre-dose, at the mid-point (1 hr) and at the end of 2-hr infusion of study drug on Days 1, 3, and EOT, and a single blood draw at EOS.

^j Obtained at Baseline, Day 3, when clinically indicated, at EOT, and at EOS.

^k Appendix 3

^l Appendix 4

^m Appendix 5

ⁿ Appendix 6

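### Hospital stay and total cost are counted from admission, but no eligibility criterion limits days since admission, so untreated days can enter both outcomes for anyone randomised later

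*Combined protocol and SAP*

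**What the plan says.** Sections 4.2.2 and 7.1.2 and the synopsis list "Length of stay in ICU and hospital (admission to discharge") among the secondary efficacy endpoints. The health outcomes endpoint in 4.2.3, repeated in 7.1.3 and the synopsis, is "Total healthcare costs from admission to discharge between treatment groups".

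Three places tie admission to randomisation:

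- Section 5.3 says study treatment "will begin immediately once the patient meets all inclusion/exclusion criteria at the start of hospitalization".
- The flow chart in 8.1 heads both Day 1 columns (screening, then baseline with randomisation) as admission. Its footnote to the first reads "Screening to determine eligibility (prior to randomization").
- The synopsis defines the time scale "with Day 1 being the day of randomization to assess safety".

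Eligibility is looser. Inclusion 1 in 5.4.1 asks for "Male or female hospitalized patients between 18 and 80 years of age at time of consent". Inclusion 2 accepts a current positive test, or patients who "have an existing complication secondary to SARS-CoV-2 infection which was positive within 2 weeks of entry into the study". Exclusion 8 in 5.4.2 rules out mechanical ventilation and acute lung injury at entry, but not being in ICU. No criterion mentions days since hospital or ICU admission.

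Section 9.3.2 names ANCOVA for continuous endpoints measured once after baseline and gives no covariate for earlier hospital days. It leaves precise endpoint definitions to a separate SAP, whose text is not in the combined document.

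**The concern.** Days and costs that accrue before the first dose cannot respond to treatment. If the outcome clock starts at admission and some patients are randomised days later, those days are added to the outcome. Their spread widens the standard error, and any chance difference between arms in prior stay passes directly into the estimated effect. With 30 patients per arm such differences need not be small, so an arm could look better or worse on stay or cost for a reason that predates randomisation.

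Later entry is foreseeable from the protocol itself. Section 3.2 describes the best moment to intervene as a worsening on the ordinal scale from hospitalised on supplemental oxygen to non-invasive ventilation or high-flow oxygen, while allowing an earlier decision. That is a change during a hospital stay. Section 3.4 describes ARDS developing within 8 days of admission.

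**Working it through.** The plan states no standard deviation, target difference or power for stay or cost, and Section 9.1 sets the sample size by medical judgement. There is therefore no planned figure to reproduce. What follows is an illustration on assumed values.

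**Inputs**

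- n = 30 per arm (5.2, 9.1).
- SD of stay after randomisation, s_post = 7 days (assumed).
- SD of days from admission to randomisation, s_pre = 1, 2, 3 or 5 days (assumed; 0 if everyone enters on the admission day).
- Prior days independent of later stay (assumed).

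**Formulas**

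- Variance ratio, admission clock to randomisation clock: R = 1 + (s_pre / s_post)².
- Equivalent loss of patients for this comparison: 1 − 1/R.
- Standard error of the chance difference in mean prior days: s_pre × √(2/30) = 0.258 × s_pre. The 95% limits are ±1.96 times this.

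| s_pre (days) | R | Equivalent loss | SE (days) | 95% limits (days) |
|---|---|---|---|---|
| 0 | 1.00 | 0% | 0 | 0 |
| 1 | 1 + 1/49 = 1.02 | 2% | 0.26 | ±0.5 |
| 2 | 1 + 4/49 = 1.08 | 7.5% | 0.52 | ±1.0 |
| 3 | 1 + 9/49 = 1.18 | 15.5% | 0.77 | ±1.5 |
| 5 | 1 + 25/49 = 1.51 | 33.8% | 1.29 | ±2.5 |

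**Sensitivity to s_post.** With s_post from 10 down to 6 days, the variance rises by 1% to 3% at s_pre = 1 and by 25% to 69% at s_pre = 5.

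**In terms of power.** Take s_post = 8 days, two-sided 5% level and 80% power. The detectable difference from randomisation is (1.96 + 0.84) × 8 × √(2/30) = 5.79 days. Counted from admission, the SD becomes √(64 + s_pre²). The detectable difference is then 5.83, 6.18 or 6.82 days for s_pre = 1, 3 or 5, and power for 5.79 days falls to 79%, 75% or 66%.

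**ICU stay, by reasoning.** An ICU stay naturally runs from ICU entry to ICU discharge. Patients ventilated at entry are excluded and the drug is meant to prevent deterioration, so ICU stays may well begin after randomisation. Prior ICU days arise only for patients already in ICU at entry. Starting the ICU clock at Day 1 would be an error in the other direction: a patient entering ICU on Day 6 would gain 5 ward days (Days 1 to 5).

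**The case against.** The strongest reply is that the protocol intends same-day entry. Section 5.3 says so, the flow chart labels Day 1 as admission, and on that reading a clock from admission and a clock from Day 1 agree to within about a day. The two-week window in Inclusion 2 limits the date of the positive test and says nothing about time in hospital. This stands as a description of intent, and it means large values of s_pre fit poorly with the described design. It does not remove the point, because a site that enrols a patient on the tenth hospital day breaks no listed criterion.

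A reader might infer that untreated days are in fact counted for the trial population. The documents do not show that: only patients randomised after the admission day contribute any, and their number is unknown. A reader might also infer that the comparison is biased. It is not, because prior days are fixed before a blinded 1:1 allocation, so their expected difference between arms is zero.

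Two further objections have weight. The separate SAP may define the clock, so it cannot be said that the matter is unhandled; but one that starts at randomisation would have to override the protocol's stated endpoint. And cost of the whole admission is a legitimate quantity in its own right, although it is a less precise measure of what treatment changed.

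**Conclusion.** The point holds in conditional form. Hospital stay and total cost start at admission, the design text assumes that admission and randomisation coincide, and eligibility does not enforce it. For patients randomised later, untreated days and costs can enter these outcomes.

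The consequence is lost precision and possible chance imbalance. It ranges from about nil with same-day entry to a variance increase of about 2%, 8%, 18% or 51% in the main illustration. These figures rest entirely on assumed standard deviations and on independence of prior and later stay. No planned power is lost, because none was specified.

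The reach is limited: stay is one of 19 secondary endpoint items, cost is a separate health outcome, and the primary endpoint, mortality and safety analyses are untouched. For ICU stay the issue concerns only patients already in ICU at entry.

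**What to change.** - **Hospital stay:** define it from randomisation (Day 1) to discharge in the synopsis, 4.2.2 and 7.1.2. Carry the same definition into the SAP.
- **Baseline table:** report days from admission to randomisation by arm.
- **ICU stay:** count only ICU days on or after randomisation, not all days from Day 1.
- **Cost (synopsis, 4.2.3, 7.1.3):** count from Day 1 where dated resource data allow. Otherwise keep whole-admission cost and adjust for days from admission to randomisation.

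For hospital stay this is a change of wording. The present endpoint already needs admission and discharge dates, although the visit lists in 8.2 name no field for them, and the randomisation date is Day 1. Cost may need more work: the flow chart and Section 8.2.6 record resource use only at end of study, and the text does not say whether items are dated. The downside is small. Whole-admission totals would no longer be the main summary, but they can still be given descriptively. If entry proves to be same-day, the results will barely change.
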